7.8. Bystander and Environmental Exposure Analyses

The bystander and environmental analysis will be analyzed and presented in a separate report.

8. PHARMACOKINETIC ANALYSES

8.1. Overview of Planned Pharmacokinetic Analyses

The PK analyses will be based on the "Systemic Pharmacokinetic Concentration" population for the plasma drug concentration data, and "BAL PK Population" for the lung ELF concentration data, unless otherwise specified.

Table 4 provides an overview of the planned analyses, with full details being presented in Appendix 11: List of Data Displays.

Table 4 Overview of Planned Pharmacokinetic Analyses

| Endpoints | | | Untr | ransfo | rmed | | | ormed | d | | | | | |
|------------------------------------|------|-------|-------|--------|-------------------|-----------------|------------|-------|----------------|-----------------|---|-----------------|------------|---|
| | Stat | s Ana | lysis | Sum | Summary | | Individual | | Stats Analysis | | | mary | Individual | |
| | T | F | L | T | F | F | L | Т | F | Ш | Т | F | F | L |
| Plasma Drug Concentrations | | | | Y | Y [1] [2] [3] [4] | Y [1] | Υ | | | | | Y [1] [2] | Y [1] | |
| Derived PK Parameters | Υ | | | Υ | | | Υ | Υ | Y [7] | Y [8] | | | | |
| Lung ELF CCI15106 Concentration | | | | Υ | Y [5] | Y [6] | Υ | | | | | | Y [1] | |

NOTES:

- T = Table, F = Figure, L = Listings, Y = Display generated.
- Stats Analysis = Represents TFL related to any formal statistical analyses (i.e. modelling) conducted.
- Summary = Represents TFL related to any summaries (i.e. descriptive statistics) of the observed raw data
- Individual = Represents FL related to any displays of individual participant observed raw data.
- 1. Linear and Semi-Log plots will be created on the same display.
- 2. Separate Mean (± SD) and Median plots will be generated, for the BD cohorts, overlay the day 1 and day 14 on same plot where possible.
- 3. Mean (± SD) and Median plots by cohorts a) to compare over the first 12hours for 60mg in HV (part 1) and COPD (part 2); b) to compare the 60mg SD (over 24h) HV vs COPD; c) to compare the 60mg BD HV vs COPD one for each of the intense sampling day (day 1, day 14).
- 4. Boxplot of plasma drug concentration at the follow up visit by cohort.
- 5. Boxplot of Lung CCI15106 concentration by cohort (HV vs COPD).
- 6. Lung CCI15106 concentration by Subject ID.
- 7. Dose proportionality of single and repeat dose and accumulation ratios from Cohorts A and B will be evaluated in Part 1 and Part 2.
- 8. Supportive SAS Output from Statistical Analysis of Loge-transformed Plasma PK Parameters.

8.1.1. Drug Concentration Measures

Refer to Appendix 4: Data Display Standards & Handling Conventions.

8.1.1.1. Derivation of Lung ELF Drug (CCI15106) Concentration Data

Urea concentration data will be used to calculate the dilution effect of the BAL A correction for dilution will be applied to all BAL drug concentrations as follows:

$$Lung\ Drug\ Concentration(ng/mL) = \frac{BAL}{Drug\ Concentration}(ng/mL) \times DilutionFactor$$

where

$$Dilution\ Factor = \frac{Plasma\ Urea_{pre-BAL}}{BAL\ Urea}$$

| C _{max} | Maximum observed concentration in plasma (ng/mL), determined directly from the concentration-time data. |
| t _{max} | Time to reach C _{max} (h), determined directly from the concentration-time data. |
| t _{1/2} | Apparent terminal half-life (h) will be calculated as: |
| | $t_{1/2} = \ln 2 / \lambda_z$ |
| λz | Apparent terminal rate constant (1/h), determined by linear regression of the terminal points of the log-linear concentration-time curve. Visual assessment will be used to identify the terminal linear phase of the concentration-time profile. A minimum of 3 data points will be used for determination. |
| CL/F | Apparent inhaled plasma clearance after dosing (L/h), calculated as administered dose divided by $AUC(0-\infty)$. |

NOTES:

Additional parameters may be included as required.

Table 6 Derived Pharmacokinetic Parameters (Cohort A, Part 1, Cohorts B, Part 1 and Part 2 – Repeat Dose)

| Parameter | Parameter Description |
|------------------|--|
| AUC(0-τ) | Area under the concentration-time curve in the plasma during a dosing interval (ng·h/mL) on day 1 and day 14, calculated by linear up/log down trapezoidal summation. Actual elapsed time at the end of the dosing interval will be used for the calculation. τ =12 for BID dosing regimen |
| C _{max} | Maximum observed concentration in plasma (ng/mL), determined directly from the concentration-time data. |
| t _{max} | Time to reach C _{max} (h), determined directly from the concentration-time data. |
| t _{1/2} | Apparent terminal half-life (h) will be calculated as: $t_{1/2} = \ln 2 / \lambda_z$ |
| λ _z | Apparent terminal rate constant (1/h), determined by linear regression of the terminal points of the log-linear concentration-time curve. Visual assessment will be used to identify the terminal linear phase of the concentration-time profile. A minimum of 3 data points will be used for determination. |

NOTES:

Additional parameters may be included as required.

Individual lung ELF concentration data will be summarised, listed and displayed graphically on both linear and semi-logarithmic scales for the Cohorts with available ELF data. Where data permit, the individual lung ELF concentration data may be plotted against the plasma concentration measured prior to BAL sampling.

8.1.2.2. Statistical Analysis of Pharmacokinetic Parameters

Geometric mean will be included for PK parameters, wherever applicable.

The following PK statistical analyses will only be performed, if sufficient data is available (i.e. if participants have well defined plasma profiles).

Pharmacokinetic Statistical Analyses

Endpoint(s)

- All endpoints, except tmax and %AUCex, will be natural-log transformed prior to the analysis
- Dose Proportionality: AUC₍₀₋₂₄₎ or AUC₍₀₋₄₈₎, or AUC_(0-τ) and Cmax, for single dose and repeat dose of Part 1
- Steady State Assessment in BID dosing: Ctrough (using pre-dose concentration from day 6 in Cohort A Part 1, and day 2 onwards in Cohorts B, Part 1 and Part 2)
- Accumulation in BID dosing: accumulation ratio will be calculated for AUC_(0-τ) as [AUC_(0-τ), on Day 19/AUC_(0-τ), on Day 6 for Cohort A in Part 1, or AUC_(0-τ) on Day 14/AUC_(0-τ) on Day 1 for Cohorts B of both Part 1 and Part 2, from the ANOVA model

Model Specification

Dose Proportionality will be assessed separately by means of power model: y = α*dose^β where y
denotes the PK parameter being analyzed. PK parameters will be normalized to 60mg dose and then
log transformed prior to analysis

If the power model does not show dose proportionality then pairwise analysis of variance (ANOVA) may be used as an exploratory analysis to understand the dose where dose proportionality fails

- Analysis of variance (ANOVA), considering study Day as fixed effect and subject as a random effect in
 the model, will be performed using SAS Mixed Linear Models procedure to evaluate in the assessment
 of steady state in models included at least 3 days of pre-dose concentrations (like Days 4,6,8; Days
 6,8,10, Days 10,12,14 relative to first dose of repeat dosing). This will be done for each of the repeat
 dose treatments.
- Analysis of variance (ANOVA), considering study Day as fixed effect and subject as a random effect in
 the model, will be performed using SAS Mixed Linear Models procedure to evaluate in the assessment
 accumulation, where geometric least squares mean ratio of AUC_(0-τ) on Day 19/AUC_(0-τ) on Day 6 for
 Cohort A in Part 1, AUC_(0-τ) on Day 14/AUC_(0-τ) on Day 1 for Cohorts B and 90% CI will be calculated.

Note: Subjects will be fit as a fixed effect for the assessment of accumulation if the model fails to converge.

Estimates of within-subject variability for Cmax, t1/2, AUC_(0-r) and CL/F will be provided, where CVw(%) = SQRT(exp(MSE) – 1)×100 and MSE is the residual mean squared error from the model. CVw represents a pooled measure of within-subject variability in repeat dose group.

Model Results Presentation

- Dose Proportionality: The intercept α and the slope β with corresponding 90% CIs will be estimated and presented for each PK parameter
- Steady State Assessment: Estimated slope parameter with 90% CI will be presented.
- Accumulation and Time Invariance: Geometric means with 90% CIs by parameter and day will be
 presented. Ratio of geometric means with corresponding 90% CIs for Day 14/ Day 1 for Cohort B or
 Day 19/Day 6 for Cohort A of Part 1 will also be presented.
- Comparative Plot of Individual Plasma PK Parameter Versus Treatment will be generated.
- Individual and box plots of Pre-dose concentrations will be generated.
- The SAS output from the statistical models will be included in a listing of supportive SAS output.

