11.4.3. Reporting Standards for Pharmacokinetic

| Pharmacokinetic Con | Pharmacokinetic Concentration Data | | | | | | |
|---|--|--|--|--|--|--|--|
| PC Windows Non- Linear (WNL) File | PC WNL file (CSV format) for the non compartmental analysis by Clinical Pharmacology Modelling and Simulation function will be created according to [Insert document name]. Note: Concentration values will be imputed as per GUI_51487 | | | | | | |
| Descriptive Summary Statistics, Graphical Displays and Listings | Refer to IDSL PK Display Standards. Refer to IDSL Statistical Principle 6.06.1. Note: Concentration values will be imputed as per GUI_51487 for descriptive summary statistics/analysis and summarized graphical displays only. | | | | | | |
| Pharmacokinetic Parameter Data | | | | | | | |
| Descriptive Summary Statistics (Log Transformed) | N, n, geometric mean, 95% CI of geometric mean, standard deviation (SD) of log-transformed data and between geometric coefficient of variation (CVb (%)) will be reported. [1] CV_b (%) = $\sqrt{\exp(SD^2) - 1}$ * 100 (SD = SD of log transformed data) | | | | | | |
| Parameters Not Being Log Transformed | N, n, geometric mean, 95% CI (Lower, Upper), standard deviation (SD), median, minimum and maximum | | | | | | |
| Listings | Interval, number of observations included in calculation of lambda_z, regression coefficient and percent AUC extrapolated (%AUCex) | | | | | | |

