|-----------|---|----------|-------|--------|--|--|--|--|
| Parameter | n | Estimate | SE | 90% CI | | | | |

Note(s): CI = confidence interval; SE = standard error.

Source: SAS Output XX

CONFIDENTIAL 205822

Example : PK_T3 Page 1 of n
Protocol : 205822

Population : Systemic PK

Table 3.1.17
Summary of Assessment of Accumulation (Part 1 and Part 2)

| | | | | | Geometric | Ratio of | | |
|-------|-----------|-------|---|-----------|-----------|-----------|--------|---------|
| Dose | Parameter | Study | | Geometric | LS Mean | Geometric | | |
| Level | (unit) | Day | n | LS Mean | 95% CI | Means | 90% CI | p-value |

Note(s): LS = least squares; CI = confidence interval.

Accumulation was assessed using a linear mixed effects model with day as a fixed effect and subject as a random effect.

205822

Source: SAS Output XX

Example : SAFE_L1 Page 1 of n

Protocol : 205822

Population : Safety (Part 1)

Listing 59
Listing of Spirometry Values – Part 1

| | | | | | | | Spirometry | 7 | | | |
|--------|-------|-------|------|-------|---------|---|------------|-----------|---|---------|------------|
| | | | | Time | | | | | | | |
| | Visit | | | of | | | | | | | |
| Cohort | / | | | first | | | | | | | |
| / | Study | Visit | | exhal | | | | | | Highest | |
| Subj. | Day | date | Test | ation | Reading | 1 | Reading 2 | Reading 3 | 3 | reading | %predicted |

205822

Source: SAS Output XX

Example : SAFE_L2 Page 1 of n

Protocol : 205822

Population : Safety (Part 1)

[figure not shown]
Listing 62
Listing of Telemetry Values – Part 1

| Cohort | Visit / | | | | | | |
|--------|------------|-------|---------|---------|---------|---------|------------------|
| / | _ | Visit | | Time | Date | Time | |
| Subj. | Day | date | started | started | stopped | stopped | Telemetry Result |

Example : PK_F1

Protocol : 205822 Population : Systemic PK

Figure xxx: CCI15106 trough Plasma Concentration versus Study Day (Part 2)

Example : PK_F2

Protocol : 205822 Population : BAL PK

Figure XXX Scatter Plot of Lung Drug Concentration versus Subject ID (Part 1 and Part 2)

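### The fixed-subject fallback for accumulation should be limited to the day ratio: it leaves between-subject variance out of the daily geometric mean CIs in Table 4.7

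*SAP*

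**What the plan says.** SAP Section 8.1.2.2, Model Specification, plans the accumulation analysis of log AUC(0-τ) by ANOVA "considering study Day as fixed effect and subject as a random effect in" the model. A note beneath it gives the fallback: "Subjects will be fit as a fixed effect for the assessment of accumulation if the model fails to converge".

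Model Results Presentation in the same section lists two outputs from this assessment:

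- each day's level: "Geometric means with 90% CIs by parameter and day will be" presented;
- the contrast: "Ratio of geometric means with corresponding 90% CIs for Day 14/ Day 1 for Cohort B or"; the sentence then names the equivalent for Part 1 Cohort A, which is Day 19 over Day 6.

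Both appear in Table 4.7 (Section 11.10.6), laid out in shell PK_T3 (Appendix 11). The shell's columns end "LS Mean | 95% CI | Means | 90% CI | p-value", so the daily LS means carry a 95% interval there but a 90% interval in Section 8.1.2.2. The shell's only model footnote reads "Accumulation was assessed using a linear mixed effects model with day as a fixed effect and subject as a random effect", with no variant for the fallback.

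Separately, Section 11.4.3 plans descriptive summaries of the log-transformed PK parameters, starting with "N, n, geometric mean, 95% CI of geometric mean, standard deviation (SD) of log-transformed data". These feed Table 4.4.

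**The concern.** The ratio compares two days within the same participants. Between-subject differences cancel from it, so treating subject as fixed does no harm. A daily mean is a different kind of quantity. With subject random, its interval says where the mean of the population sampled may lie. With subject fixed, it says only how precisely the average of these particular participants was measured. One table column would therefore change its meaning because of a numerical event in fitting, while the footnote went on calling subject random.

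What is at stake is the honesty of the error bars around daily exposure in Table 4.7. The accumulation estimate itself is not at stake.

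**Working it through.** The SAP gives no variance or planning figure for this analysis, so there is no figure of its own to reproduce.

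**Inputs**

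- Model, fallback and reported quantities: SAP Section 8.1.2.2 and shell PK_T3.
- n = 6 and 12: these appear in the example shells of Appendix 11 and are used only as illustration.
- Within-subject CV (CVw) 20% and between-subject CV (CVb) 10% to 60%: assumptions, because the SAP gives neither.
- Two days per participant, complete pairs.

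**Standard errors.** On the log scale, let s² = ln(1 + CV²), with sb² between and sw² within subjects. The SAP's own definition, "MSE is the residual mean squared error from the model", makes MSE the estimate of sw².

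- Daily mean, subject random: √((sb² + sw²)/n)
- Daily mean, subject fixed: √(sw²/n)
- Log ratio of the two days: √(2·sw²/n) under both

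The width of the daily CI, fixed relative to random, is k = √(sw²/(sb² + sw²)).

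**Coverage.** A daily mean is independent of MSE, which has n − 1 degrees of freedom here. The fixed-subject interval therefore covers the population mean with probability P(|T| ≤ t·k), where T has n − 1 degrees of freedom. For a nominal 90% interval t is 2.015 (n = 6) or 1.796 (n = 12).

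Example, CVb 30%, n = 6: sb² = ln 1.09 = 0.0862 and sw² = ln 1.04 = 0.0392. Then k = √(0.0392/0.1254) = 0.559, and P(|T| ≤ 2.015 × 0.559 = 1.126) = 0.689.

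| CVb (CVw 20%) | k | 1/k | Coverage of nominal 90%, n=6 | n=12 |
|---|---|---|---|---|
| 10% | 0.89 | 1.12 | 87% | 86% |
| 20% | 0.71 | 1.41 | 79% | 77% |
| 30% | 0.56 | 1.79 | 69% | 66% |
| 40% | 0.46 | 2.19 | 60% | 57% |
| 60% | 0.34 | 2.97 | 47% | 44% |

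Simulation agrees with these values. In the same simulations a t interval from each day's own log-scale SD covered 90% throughout. The fixed-subject CI of the ratio also covered 90% in every setting simulated (CVb up to 50%).

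Over a wider assumed range, k runs from 0.95 (CVb 10%, CVw 30%) to 0.14 (CVb 80%, CVw 10%).

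**One fitted data set** (n = 12, CVb 40%, CVw 15%): the SE of the Day 1 LS mean was 0.031 with subject fixed and 0.110 with subject random. The SE of the Day 14/Day 1 log ratio was 0.0445 under both.

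**Allowing for the trigger.** The table above averages over all data sets, but the fallback acts only on non-convergence. One plausible cause is a between-subject variance estimated at zero. Restricting 400,000 simulated data sets per setting to those with a zero estimate (CVw 20%) gives:

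| CVb | Zero estimate occurs, n=6 / n=12 | Coverage given zero estimate, n=6 / n=12 |
|---|---|---|
| 10% | 33% / 25% | 94% / 93% |
| 20% | 13% / 4% | 90% / 87% |
| 30% | 4% / 0.5% | 84% / 80% |
| 40% | 1.7% / 0.06% | 76% / 73% |

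In data sets with a zero estimate the fixed-subject interval is not narrower than the random-subject one (median width ratio 1.03 to 1.15).

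**The case against.** The case for leaving the note alone is substantial.

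- **It will seldom operate, and then mildly.** With two days, one random intercept and complete pairs, the REML fit has a closed form. The main numerical difficulty is a zero variance estimate, which software may not even report as non-convergence. The settings with the worst coverage are those in which a zero estimate hardly ever occurs. This stands and is the main reason for low severity. However, the note names no cause, other causes such as incomplete pairs are possible, and some shortfall remains at CVb 30% and above.
- **Correct daily intervals exist elsewhere.** Table 4.4 gives each day's geometric mean with a 95% CI from the ordinary SD. This also stands, but it does not make the Table 4.7 column right.
- **Tables 4.4 and 4.7 would differ anyway.** The random-subject model pools variance over days, and the text sets a different confidence level. So a mismatch between the tables is not by itself evidence against the fallback.
- **Nothing is decided on these intervals.** Section 2.4 states that no hypotheses will be tested, and accumulation is defined as the ratio. This stands.
- **The shell is only an example, and the SAS output will be listed.** True, but a reader of Table 4.7 would still be told that subject was random when it was not.

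A reader might infer that the fallback undermines the accumulation result. It does not: the ratio is a within-subject contrast and is unchanged with complete pairs. A reader might also infer that the daily intervals would be far too narrow. The SAP gives no CVs to support that, and at CVb 10% with CVw 30% they are only about 5% narrower.

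**Conclusion.** The point holds, at low severity. As written, the fallback covers the whole accumulation assessment. Under it, the daily geometric mean CIs in Table 4.7 omit between-subject variance, and the PK_T3 footnote becomes untrue. The direction is certain whenever participants differ: relative to what a population mean requires, the intervals are on average too narrow.

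The size is not fixed by the document. On the assumed CVw of 20% and n of 6 or 12, a nominal 90% interval covers between about 87% (CVb 10%) and 44–47% (CVb 60%) before allowing for the trigger. Where the trigger is a zero variance estimate, coverage is close to or above nominal at CVb 10% to 20% and falls to 80–84% at 30%.

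The ratio and its 90% CI, which are the accumulation result, are unaffected with complete pairs. The conflict between 90% and 95% for the daily intervals is present whether or not the fallback is used.

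**What to change.** Replace the note in Section 8.1.2.2 with wording to this effect:

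> *If the mixed model does not converge, the ratio of geometric means and its 90% CI will be taken from a model with day and subject as fixed effects, using participants with data on both days. Each day's geometric mean and CI will then be calculated from the mean and SD of the log-transformed values on that day (t interval), as in Table 4.4.*

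Make the PK_T3 footnote conditional, so that it names the model actually fitted and, under the fallback, the source of the daily intervals. If some pairs are incomplete, it should also say that the ratio and the daily means rest on different participants.

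In the same edit, choose one confidence level for the daily means and use it in both Section 8.1.2.2 and PK_T3. Choosing 95% would make the fallback intervals directly comparable with Table 4.4.

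The cost is the replacement note, a conditional footnote and one column heading or level. No new data or additional analysis is needed.

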9. POPULATION PHARMACOKINETIC (POPPK) ANALYSES

Population pharmacokinetics modelling may be conducted and reported separately.

The detailed PopPK methodology will be described in a separate RAP where appropriate. The required data for the analyses are provided in Appendix 8: Population Pharmacokinetic (PopPK) Analyses and are subject to delivery soon after DBF.

11.2. Appendix 2: Schedule of Activities

11.2.1. Protocol Defined Schedule of Events

Screening and follow-up procedures for all cohorts

| Procedure | Screening, ≤ 30 days before D1 for Part 1 or ≤ 45 days before D1 for Part 21 | Follow up 30±2 days after the last dosing day | Notes |
|---|--|---|--|
| Informed consent | Х | | Screening assessments can be performed over multiple screening visits |
| Inclusion and exclusion criteria | X | | If test otherwise performed within 3 months prior to first dose of study treatment, testing |
| Demography | X | | at screening is not required |
| Full physical examination including height and weight, oral examination | Х | | To be drawn fasting (for at least 8 h) To be administered to participants with COPD only, 15-30 minutes prior to spirometry |
| Brief physical examination, oral examination | | Х | To be done at screening for participants with COPD only, following salbutamol dosing To be performed in the bronchoalveolar lavage (BAL) cohorts only to confirm participant |
| Medical history (includes substance usage and Family history of premature CV disease) | х | | eligibility 7. To be performed in the BAL cohorts only to confirm participant eligibility. Can be done pre-dose on Day -1 instead, if required |
| Substance testing (drugs, alcohol) | X | | |
| Assessment of child-bearing potential for females | Х | | |
| Serum pregnancy test in women | X | X | |
| Human immunodeficiency virus (HIV), Hepatitis B (Hep B) and Hepatitis C (Hep C) screen ² | Х | | |
| Haematology, clinical chemistry and urinalysis (include liver chemistries) ³ | Х | X | |
| Salbutamol administration ⁴ | X | | |
| Spirometry ⁵ | X | | |
| 12-lead ECG and vital signs | Х | X | |
| Coagulation parameters ⁶ | X | | |
| Capillary pCO ₂ ⁷ | X | | |
| PK blood sample | | X | |
| AE review | | X | |
| SAE review | X | X | |
| Concomitant medication review | X | X | |

Schedule for Cohort A Part 1

| Procedure | | | | | | | | | | Tre | eatmer | nt Peri | od, Da | ıys | | | | | | | | | |
|---|----|------------------|-----------------|------------|---|---|----|----|-----------------------|----------------|----------------|----------------|--------|-----|----------------|----------------|----|----|----------------|----|----|--------------|----|
| | -1 | 11 | 2 | 31 | 4 | 5 | 6 | 7 | 8 | 9 | 10 | 11 | 12 | 13 | 14 | 15 | 16 | 17 | 18 | 19 | 20 | 21 | 22 |
| Inclusion and exclusion criteria | Х | | | | | | | | | | | | | | | | | | | | | | |
| Brief physical examination, oral examination | Χ | | | | | | | | | | | | | | | | | | | | | | Х |
| Substance testing (drugs, alcohol, tobacco) | Χ | | | | | | | | | | | | | | | | | | | | | | |
| Inhaler device training ² | Χ | | | | | | | | | | | | | | | | | | | | | | |
| Serum pregnancy test in women | X | | | | | | | | | | | | | | | | | | | | | | |
| Admittance to clinic | X | | | | | | | | | | | | | | | | | | | | | | |
| Randomization | X3 | | | | | | | | | | | | | | | | | | | | | | |
| Discharge | | | | | | | | | | | | | | | | | | | | | | | X4 |
| Haematology, clinical chem and urinalysis (include liver chem) ⁵ | Χ | | Χ | | | χ | | | | | | | Χ | | | | | | | | | | Х |
| Spirometry | | X1 | | X1 | | | X6 | | X ⁷ | | | X7 | | | | | X7 | | | Χ6 | | | |
| Telemetry (starting 30 min pre-morning dose and continuous at least 4h post-morning dose) | | X 1 | | X 1 | | | Х | | | | | | Х | | | | | | X | | | | |
| 12-lead ECG and vital signs | XX | Χ¹ | | Χ¹ | | | X8 | | X8 | X8 | | X8 | X8 | X8 | | Χ8 | | X8 | | | | | |
| CCI15106-IP or placebo treatment, device incident assessment | | X1 | | X1 | | | X9 | X9 | X9 | X ⁹ | X ⁹ | X ⁹ | X9 | X9 | X ⁹ | X ⁹ | X9 | X9 | X ⁹ | X9 | | | |
| PK blood sample ¹⁰ | | Χ | Χ | Χ | Χ | Х | Χ | Χ | | Χ | | Χ | | Х | | Χ | | Χ | | Χ | Χ | Χ | Х |
| AE review | | | (-== | | | | | | | | | | | | | | | | | | | - | |
| SAE review | | (=== | | | | | | | | | | | | | | | | | | | |) | , |
| Concomitant medication review | | (=== | | | | | | | | | | | | | | | | | | | | - | |

- 1. Single dose days. Follow schedule for Day 1 of Part 2 Cohort A
- 2. Day -1 inhaler training may be done on Day 1 instead, before the first dose administration. Other time-points may be added per investigators discretion.
- 3. Can be performed on Day 1 prior to dosing
- 4. After all procedures and assessments are complete
- 5. To be drawn fasting (for at least 8 h)
- 6. To be performed at the following timepoints in the mornings only: pre-dose, and 0.25, 0.5, 1, 4 h post-dose
- 7. To be performed at the following timepoints in the mornings only: pre-dose and 4 h post-dose
- 8. ECG and vital signs to be obtained 2 h after the morning dose
- BI
- 10. PK samples on days 1, 3, 6, and 19 will be collected at the following timepoints: pre-dose, 0.25, 0.5, 0.75, 1, 2, 4, 6, 8, 10, 12 h. On day 2, one sample in the morning (24h post day 1 dose). On days 4 and 5, one sample on each morning (24h and 48h post day 3 dose). On days 6 and 19, the evening dose will be given after 12 h post-dose sample is collected. On all other days, PK sample will be collected once, before the morning dose (if on dosing days).

Schedule for Cohort A Part 2 (and all other single dose administrations)

| | Treatment Period, Days (D) and hours (h) | | | | | | | | | | | | | |
|---|--|---|----|-------|------|-------|----|----|----|----|----|-----|-----|-----------------|
| | D-1 D1 | | | | | | | | | | | | | D2 |
| Procedure | | Pre- dose | 0h | 0.25h | 0.5h | 0.75h | 1h | 2h | 4h | 6h | 8h | 10h | 12h | 24h |
| Inclusion and exclusion criteria | Х | | | | | | | | | | | | | |
| Brief physical examination, oral examination | X | | | | | | | | | | | | | Х |
| Substance testing (drugs, alcohol) | X | | | | | | | | | | | | | |
| Serum pregnancy test in women | X | | | | | | | | | | | | | |
| Admittance to clinic | X | | | | | | | | | | | | | |
| Inhaler device training ¹ | Х | | | | | | | | | | | | | |
| Randomization | Х2 | | | | | | | | | | | | | |
| Discharge | | | | | | | | | | | | | | Х3 |
| Haematology, clinical chem and urinalysis (include liver chem)4 | X | | | | | | | | | | | | | Χ |
| Spirometry | | X5 | | X6 | Χ | | Χ6 | | X6 | | | | | |
| Telemetry | | 30 min pre-dose and continuous until at least 4 h | | | | | | | | | | | | |
| 12-lead ECG and vital signs | | XXX | | X | | | Χ | X | X | | Χ | | Χ | |
| CCI15106-IP or placebo treatment | | | Х | | | | | | | | | | | |
| PK blood sample ⁷ | | Х | | Х | X | X | Х | Х | Х | Χ | Х | Х | X | Х |
| AE review | ← | | | | | | | | | | | | | |
| SAE review | (| | | | | | | | | | | | | |
| Concomitant medication review | (====== | | | | | | | | | | | | | > |

- 1. Day -1 inhaler training may be done on Day 1 instead, before the first dose administration. Other time-points may be added per investigators discretion
- 2. Can be performed on Day 1 prior to dosing
- 3. After all assessments are completed
- 4. To be drawn fasting (for at least 8 h)
- 5. To be performed within 15 to 60 minutes pre-dose
- 6. To be performed after ECG, VS and PK blood draw are obtained
- 7. Additional PK collection time points may be added to better characterize the PK profile

Repeat dose schedule to be followed for repeat dose cohorts in Parts 1 and 2 (other than Cohort A Part 1)

| Procedure | | | | | | | Trea | tment P | eriod, [| Days | | | | | | |
|---|----------------|------------|---|----|---|---|------|---------|----------|------|-----|----|-----|----------------|----|-----------------|
| | -1 | 1 | 2 | 3 | 4 | 5 | 6 | 7 | 8 | 9 | 10 | 11 | 12 | 13 | 14 | 15 |
| Inclusion and exclusion criteria | X | | | | | | | | | | | | | | | |
| Brief physical examination, oral examination | X | | | | | | | | | | | | | | | X |
| Substance testing (drugs, alcohol, tobacco1) | X | | | | | | | | | | | | | | | |
| Inhaler device training ² | X | | | | | | | | | | | | | | | |
| Serum pregnancy test in women | X | | | | | | | | | | | | | | | |
| Admittance to clinic | X | | | | | | | | | | | | | | ĺ | |
| Randomization | X ₃ | | | | | | | | | | | | | | 1 | |
| Discharge | | | | | | | | | | | | | | | ĺ | X4 |
| Dosing procedure training with bystanders | | X5 | | | | | | | | | | | | | 1 | |
| Haematology, clinical chem and urinalysis (include liver chem)6 | Х | | | | | | | Х | | | | | | | | Х |
| Spirometry | | X 7 | | Χ8 | | | χ8 | | | | | Χ8 | | | Х7 | |
| Telemetry (starting 30 min pre-morning dose and continuous at least 4h post-morning dose) | | Х | | | | | | Х | | | | | | X ⁹ | | |
| 12-lead ECG and vital signs ¹⁰ | XXX | Χ | | Χ | Χ | | Х | Х | Χ | | X11 | | X11 | | ĺ | |
| CCI15106-IP or placebo treatment BID, device incident assessment BID ¹² | | Х | Х | Х | Х | Х | Х | Х | Х | Х | Х | Х | Х | Х | Х | |
| PK blood sample ¹³ | | Χ | Х | | Χ | | Х | | Χ | | Х | | Х | | Х | X |
| BAL | | | | | | | | | | | X14 | | | | | |
| Urea blood sample | χ15 | | | | | | | | | | | | | | | |
| AE review | () | | | | | | | | | | | | | | | |
| SAE review | | | | | | | | | | | | | | | | |
| Concomitant medication review | (| | | | | | | | | | | | | | | > |

- 1. Tobacco test to be performed only in healthy participants
- 2. Day -1 inhaler training may be done on Day 1 instead, before the first dose administration. Other time-points may be added per investigators discretion.
- 3. Can be performed on Day 1 prior to dosing
- 4. After all procedures and assessments are complete
- 5. To be done only in Cohort(s) where bystanders are present. Can be performed on Day -1 instead, if desired. Other time-points may be added per investigators discretion.
- 6. To be drawn fasting (for at least 8 h)
- 7. To be performed at the following timepoints in the mornings only: pre-dose, and 0.25 (in participants with COPD only), 0.5, 1, 4 h post-dose
- 8. To be performed at the following timepoints in the mornings only: pre-dose and 4 h post-dose

- 9. Telemetry may be performed on Days 11 or 12 instead, not to coincide with the BAL procedure.
- 10. ECG and vital signs to be obtained 2 h after the morning dose
- 11. When BAL is performed, vital signs and ECG will be performed before and after the procedure and oxygen saturation will be measured continuously.
- 12. For cohort with bystanders, BID doses may have ±1.5 h window.
- 13. PK samples on days 1 and 14 will be collected at the following timepoints: pre-dose, 0.25, 0.5, 0.75, 1, 2, 4, 6, 8, 10, 12 h. The evening dose will be given after 12 h post-dose sample is collected. On all other days, PK sample will be collected once, before the morning dose. When BAL is performed, one additional PK sample will be collected after dosing immediately prior to bronchoscopy
- 14. Done once during these four days, as soon as possible (within 1 h) after the first dose of the day
- 15. To be collected immediately before bronchoscopy

Schedule for Cohort C Part 1 (bystanders and air monitoring), to be executed concomitantly with Cohort B Part 1

| Procedure Treatment Period, Days | | | | | | | | | | | | | | | | |
|---|----------------|----------------|---|-----------------------|----|--------------------|-------------------|----------------|----|---|-----------------------|----|----|----|----------------|----|
| | -1 | 1 | 2 | 3 | 4 | 5 | 6 | 7 | 8 | 9 | 10 | 11 | 12 | 13 | 14 | 15 |
| Inclusion and exclusion criteria | X | | | | | | | | | | | | | | | |
| Brief physical examination, oral examination | X | | | | | | | | | | | | | | | Х |
| Substance testing (drugs, alcohol, tobacco) | Х | | | | | | | | | | | | | |] | |
| Serum pregnancy test in women | Х | | | | | | | | | | | | | | | |
| Admittance to clinic | X | | | | | | | | | | | | | | | |
| Discharge | | | | | | | | | | | | | | | | X1 |
| Training ² | X | | | | | | | | | | | | | | | |
| Haematology, clinical chem and urinalysis (include liver chem)3 | X | | | | | | | Χ | | | | | | | | Χ |
| Exposure to dosing | | Χ | Χ | X | Χ | X | X | X | Χ | X | Χ | X | X | X | Χ | |
| PK blood sample | | X ⁴ | | | | | | X ⁴ | | | | | | | X ⁴ | X |
| Stationary pump air monitoring ⁵ | | Χ | | | | | | Χ | | | | | | | Χ | |
| Personal exposure pump monitoring ⁶ | | Χ | | | | | | Χ | | | | | | | Χ | |
| 12-lead ECG and vital signs | XXX | X7 | | X ⁷ | χ7 | | χ7 | X7 | X7 | | X ⁷ | | X7 | | | |
| AE review | ←) | | | | | | | | | | | | | | | |
| SAE review | ← | | | | | = -> | | | | | | | | | | |
| Concomitant medication review | (| | | | | | = > | | | | | | | | | |

- 1. After all procedures and assessments are complete
- 2. Day -1 training may be done on Day 1 instead, before the first dose administration. Other time-points may be added per investigators discretion
- 3. To be drawn fasting (for at least 8 h)
- 4. PK samples will be collected pre-dose and 15 min after the dosing participant takes their first daily dose. In addition, on days 7 and 14, one sample on each day will be collected before the dosing participant takes the first daily dose. On day 15, one sample will be collected before discharge.
- 5. Samples of air to be collected for 20 and 60 min during and after the first morning dose
- 6. Samples of air to be collected for 15 min during and after the first morning dose
- 7. ECG and vital signs to be obtained 2 h after the exposure to morning dose

